1.3 Randomization

[figure not shown]
[figure not shown]
A member of the Randomization Programming group at Alcon who is not part of the study team will generate the randomized allocation schedule(s) for study lens sequence assignment. Randomization will be implemented in the Electronic Data Capture (EDC)/randomization integration system.

Qualifying subjects will be randomized in a 1:1 ratio to receive treatment (lens) in crossover sequence as follows:

Sequence		Lens Name
Sequence 1		PRECISION1/Biotrue
Sequence 2		Biotrue/PRECISION1

1.4 Masking

This study is double-masked.

2 ANALYSIS SETS

2.1 Safety Analysis Set

Safety analyses will be conducted using the safety analysis set on a treatment-emergent basis. As such, the safety analysis set will include all subjects/eyes exposed to any study lenses evaluated in this study.

For treatment-emergent safety analyses, subjects/eyes will be categorized under the actual study lenses exposed in the corresponding lens sequence.

Adverse events occurring from the time of informed consent but prior to first exposure to study lenses will be summarized in subject listings.

2.2 Full Analysis Set

The full analysis set (FAS) is the set of all randomized subjects who are exposed to any study lenses [REDACTED] evaluated in this study.

2.3 Per Protocol Analysis Set

The per protocol (PP) analysis set is a subset of FAS and excludes all data/subjects that have met any of the critical deviation or evaluability criteria identified in the Deviation and Evaluability Plan (DEP).

3 SUBJECT CHARACTERISTICS AND STUDY CONDUCT SUMMARIES

The following tables will be presented:

- Subject Disposition by Lens Sequence
- Analysis Sets by Lens
- Analysis Sets by Lens Sequence
- Subject Accounting by Lens Sequence
- Demographics Characteristics by Lens Sequence
- Baseline Characteristics by Lens Sequence [lens brand, lens solution, power: sphere, Best Corrected Visual Acuity]

Subject accounting and demographics characteristics tables will be summarized on the safety, full, and per protocol analysis datasets. Baseline characteristics will be summarized on the full and per protocol analysis datasets.

In addition, the following subject listings will be provided:

- Listing of Subjects Excluded from Protocol Defined Analysis Sets
- Listing of Lens Sequence Assignment by Investigator
- Listing of Subjects Discontinued from Study

4 EFFECTIVENESS ANALYSIS STRATEGY

This study defines 1 primary, [REDACTED] effectiveness endpoint. [REDACTED] effectiveness evaluation [REDACTED] will use the FAS as the primary analysis set.

[REDACTED]
[REDACTED]
[REDACTED]

Continuous variables will be summarized using the number of observations, mean, standard deviation, median, minimum, and maximum, as well as confidence intervals/limits as applicable. Categorical variables will be summarized with frequencies and percentages from each category.

All data obtained in evaluable subjects/eyes will be included in the analysis. No imputation for missing values will be carried out for the primary and key exploratory effectiveness analyses.

For all planned inferential analyses, alternative models/methods may be considered, for instance, if convergence cannot be achieved. Furthermore, if significant carryover effects are noted (confounded with sequence effect), results will be examined by period to ensure the overall conclusion is valid.

A listing of select effectiveness data will also be provided.

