## 7 INVESTIGATIONAL PLAN

### 7.1 Study Design

This is a prospective, randomized, controlled, double-masked bilateral crossover, daily wear, multicenter clinical study. Habitual soft contact lens wearers will be randomized in 1 of the 2 crossover sequences. Subjects and investigators will be masked. [REDACTED]

[figure not shown]
[REDACTED]

Subjects will be expected to attend 3 visits: Screening/Baseline/Dispense Lens 1, Visit 2 (Week 1 Follow-up Lens 1/Dispense Lens 2), and Visit 3 (Week 1 Follow-up Lens 2/Exit). The total duration of a subject's participation in the study will be up to 22 days. Subjects will be expected to wear their study contact lenses daily for at least 10 hours per day.

On the day prior to Visit 2 and the day prior to Visit 3, subjects will be instructed to wear the study lenses at least 16 hours. [REDACTED] (spectacles or no lens wear) of at least 12 hours will be required after Visit 1 and after Visit 2.

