**Table 9–1 Test Product**

Test Product	PRECISION1 soft contact lenses (PRECISION1)
Manufacturer	Alcon Laboratories, Inc. [name]

	[name] USA
Indication for use and intended purpose in the current study	Precision1 (verofilcon A) spherical soft contact lenses are indicated for the optical correction of refractive ametropia (myopia and hyperopia) in phakic or aphakic persons with nondiseased eyes with up to approximately 1.50 diopters (D) of astigmatism that does not interfere with visual acuity. The lenses are to be prescribed for single use, daily disposable wear. The lenses are not intended to be cleaned or disinfected and should be discarded after a single use.
Product description and parameters available for this study	

• Material: verofilcon A

• Water content: 51%

• Power range: -1.00 to -6.00 D, 0.25 D steps

• Base curve (mm): 8.3

• Diameter (mm): 14.2

Formulation	Please refer to package insert.
Usage	

• Wear:

○ Daily Wear

○ Bilateral

• Replacement period: Daily Disposable

• Exposure:

○ 16 days total duration (test and comparator)

■ Test Product: 8 (-0/+3) days

■ Comparator Product: 8 (-0/+3) days

• Lens Care: N/A

Number/Amount of product to be provided to the subject	Subjects will be dispensed study lenses at Visit 1 and Visit 2. No spare lenses will be provided to the subject.

Packaging description	Blister foil pack
Labeling description	

• Lens Foil label includes:

- lens identifier

- base curve

- diameter

- packing solution

- power

- lot number

- expiration date

- content statement

- investigational device statement

- sponsor information

- country of origin

	
	
	
	
	
	
	
Storage conditions	Stored at room temperature.
	
	
Supply	Alcon will provide a fitting set and study lenses. Refer to the MOP for a detailed description

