1.2 Study Description

Key components of the study are summarized in Table 1-1.

Table 1-1 **Study Description Summary**

[figure not shown]
Study Design	Prospective, randomized, controlled, double-masked, bilateral crossover
Study Population	Volunteer subjects aged 18 or over who are habitual spherical soft contact lens wearers (excluding current/previous PRECISION1, Biotrue and DAILIES TOTAL1® habitual lens wearers), have at least 3 months of contact lens wearing experience, and who wear their habitual lenses at least 5 days per week and at least 10 hours per day. [REDACTED] [REDACTED] [REDACTED] [REDACTED]
	Target to complete: 116 Planned to enroll: ~128
Number of Sites	~8 US
Test Product	PRECISION1 soft contact lenses (PRECISION1) [REDACTED]

Comparator Product	Biotrue ONEday soft contact lenses (Biotrue) [REDACTED]
Planned Duration of Exposure	~16 days total duration (test and comparator): Test Product: 8 (-0/+3) days Comparator Product: 8 (-0/+3) days
Visits	Pre-Screening (optional) Visit 1: Screening/Baseline/Dispense Lens 1 [‡] Visit 2: Week 1 Follow-up Lens 1/Dispense Lens 2 [‡] [8 (-0/+3) days after Visit 1] Visit 3: Week 1 Follow-up Lens 2/Exit [8 (-0/+3) days after Visit 2] [REDACTED] [REDACTED] [REDACTED]

A study design schematic is depicted in Figure 1-1.

Figure 1-1

Study Design

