4.3 Statistical Methods for Effectiveness Analyses

4.3.1 Primary Effectiveness Analysis

A mixed effects repeated measures model will be utilized to test these hypotheses. The model will include terms for lens, period, and sequence. Within-subject correlation due to eye and the crossover design will also be accounted for in the model. Lens difference (PRECISION1 minus Biotrue) and the corresponding one-sided 95% upper confidence limit will be computed. Noninferiority in distance VA will be declared if upper confidence limit is less than 0.05.

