7 SAMPLE SIZE AND POWER CALCULATIONS

Sample size calculation is based on a prior clinical study [REDACTED] which evaluated performance of PRECISION1 and Biotrue. [REDACTED]

Primary Effectiveness

[figure not shown]
[figure not shown]
To demonstrate noninferiority (margin = 0.05 in logMAR; $\frac{1}{2}$ line in Snellen) in distance VA as a one-tailed hypothesis with $\alpha=0.05$, and using a standard deviation of 0.0462 for paired differences, 80% power can be attained with a sample size of 8 (4 per sequence).

[figure not shown]

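### Does tying the by-period look to a significant sequence effect leave the noninferiority conclusion unprotected against carryover?

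*SAP*

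**What the plan says.** SAP Section 4 (Effectiveness Analysis Strategy) contains the only visible statement on carryover: "if significant carryover effects are noted (confounded with sequence effect), results will be examined by period to ensure the overall conclusion is valid". The sentence before it is general: "For all planned inferential analyses, alternative models/methods may be considered, for instance, if convergence cannot be achieved". The visible text gives no level for the carryover test and no rule for reading a by-period result against the margin. Parts of Section 4 are blacked out and may say more.

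SAP Section 4.3.1 defines the primary analysis: "The model will include terms for lens, period, and sequence". The decision rule has no condition attached: "Noninferiority in distance VA will be declared if upper confidence limit is less than 0.05".

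Three design features bear on carryover:

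- The test lens is a daily disposable (Protocol Table 9-1): "The lenses are not intended to be cleaned or disinfected and should be discarded after a single use". The comparator has the same replacement schedule (Protocol Table 9-2).
- Protocol Section 7.1 sets a time without lenses "of at least 12 hours will be required after Visit 1 and after Visit 2".
- Visits 2 and 3, where distance acuity is read with the study lenses, fall 8 (-0/+3) days after the visit before (Protocol Section 10).

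SAP Table 1-1 gives the size: "Target to complete: 116 Planned to enroll: ~128". SAP Section 7 says that 8 subjects suffice for the primary endpoint.

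**The concern.** A conditional check of this kind is known to be weak. In a two-period crossover, the sequence effect is estimated between subjects, so it is much less precise than the lens difference. If wearing PRECISION1 first left some loss of acuity in Period 2, the Biotrue readings in that sequence would be worse and the lens difference would shrink. In a noninferiority trial that shrinkage favours success.

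Period 1 alone is a randomized comparison that carryover cannot reach. The SAP commits to examining it only when the weak test is significant. A lens at the margin could therefore pass while the check stays silent, and a non-significant sequence term might then be taken as evidence that carryover is absent.

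**Working it through.** **Inputs from the documents.** Margin 0.05 logMAR; one-sided 95% upper limit; SD of paired differences 0.0462 (SAP Section 7); 116 completers at 1:1, so 58 per sequence.

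**Assumptions, not in the documents.** One value per subject and period. Between-subject SD sb of 0.03, 0.05, 0.08 or 0.10 logMAR. Carryover L from PRECISION1 of 0.01, 0.02 or 0.03, which is 20%, 40% or 60% of a true difference of 0.05. Trigger at two-sided 0.05, with 0.10 as a sensitivity.

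**The plan's own figure.** With SE = 0.0462/√N, N − 2 degrees of freedom and a true difference of 0, power is 70.3% at N = 6 and 85.3% at N = 8. The smallest balanced total that reaches 80% is 8, as the SAP states.

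**Effect of carryover.** Let d be the true lens difference (PRECISION1 minus Biotrue; positive is worse).

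- Period 1 estimates d. Period 2 estimates d − L.
- The crossover estimate is their average, d − L/2.
- The sequence contrast of subject totals is Period 1 minus Period 2, which is L.
- With complete data, Period 1 difference = crossover estimate + half the sequence contrast.

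**Precision.** Within-subject SD sw = 0.0462/√2 = 0.0327.

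- Crossover: 0.0462/√116 = 0.0043.
- Sequence contrast: √[(2/58)(4sb² + 2sw²)] = 0.0141 / 0.0205 / 0.0309 / 0.0381 for the four values of sb, or 3.3 to 8.9 times the crossover SE.
- Period 1: √[(2/58)(sb² + sw²)] = 0.0082 / 0.0111 / 0.0160 / 0.0195.

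**Pass rate and trigger rate at d = 0.05** (t with 114 degrees of freedom). The crossover estimate and the sequence contrast are independent, so the trigger rate among passing trials is about the overall rate.

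| L | Trial passes | Trigger at 0.05, sb = 0.03 / 0.05 / 0.08 / 0.10 | Trigger at 0.10, same order |
|---|---|---|---|
| 0 | 5% | – | – |
| 0.01 | 31% | 11% / 8% / 6% / 6% | 18% / 14% / 12% / 11% |
| 0.02 | 75% | 29% / 16% / 10% / 8% | 41% / 25% / 17% / 15% |
| 0.03 | 97% | 56% / 31% / 16% / 12% | 68% / 43% / 25% / 20% |

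With the opposite sign the error runs the other way: at L = −0.02 and d = 0.05 the pass rate is about 0%.

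**What an unconditional Period 1 result would show without carryover.** The crossover analysis passes in about 100% of trials at each d below. The Period 1 upper limit is nevertheless 0.05 or more in:

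| d | sb = 0.03 | 0.05 | 0.08 | 0.10 |
|---|---|---|---|---|
| 0 | 0% | 0.2% | 7% | 18% |
| 0.01 | 0.1% | 3% | 20% | 35% |
| 0.02 | 2% | 15% | 42% | 55% |

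**The case for a change.** The strongest argument for a change is that the sponsor itself thought carryover worth a safeguard, and that the safeguard seldom operates at the sizes that matter. Showing Period 1 every time would cost one sentence and one table. It would also avoid a selection effect. In simulation with no carryover, d = 0.05 and a significant sequence test, the Period 1 limit fell below 0.05 in about 40% to 49% of trials, where an unconditional Period 1 analysis gives 5%.

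Much of this stands. The sequence test is weak, and a non-significant result is not evidence that carryover is absent. The conditional look is not a clean test either.

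The step from there to a needed change does not stand, for three reasons:

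- A descriptive table does not alter the decision. Every trial counted as a pass in the working would still pass.
- The SAP says when by-period results will be examined; it does not bar showing them otherwise. Sequence is always in the model, and with complete data the Period 1 difference follows from the lens and sequence estimates. An analyst can report it at any time.
- A Period 1 limit of 0.05 or more cannot separate carryover from imprecision. At d = 0.05 it occurs in about 95% of trials whatever the carryover. At small, truly noninferior differences it can also be common, as the second table shows.

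**Conclusion.** The concern reads the SAP correctly and its figures reproduce, but no change to the plan follows. The harm needs three things together: a true difference at the margin, carryover of roughly 20% to 60% of that difference, and the unfavourable sign. The documents give no reason to expect this. The carried-over part would have to outlast discarded lenses, at least 12 hours without lenses and 8 to 11 days on the other lens.

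Without carryover the primary estimate and the success rule are sound, with a 5% pass rate at the margin. Reporting by period in every case would gain transparency, change no decision, and raise doubts about some sound results. That false-alarm rate is 0.1% to 15% at between-subject SDs of 0.03 to 0.05, and 20% to 55% at 0.08 to 0.10, for true differences of 0.01 to 0.02. Reasonable statisticians would differ on that trade-off.

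The detection and false-alarm rates rest on assumed between-subject SDs, and the pass and detection rates on assumed carryover sizes. The point to carry forward is one of interpretation: a non-significant sequence term says little about carryover, and the case against carryover rests on the design.

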4.1 Effectiveness Endpoints

Primary Effectiveness Endpoint

The primary endpoint is distance VA with study lenses, collected for each eye in logMAR.

[REDACTED]

4.2 Effectiveness Hypotheses

[figure not shown]
Primary Effectiveness

The null and alternative hypotheses are formulated in terms of the predefined margin of 0.05 for noninferiority:

$$H_0: \mu_{(T)} - \mu_{(C)} \geq 0.05$$

$$H_a: \mu_{(T)} - \mu_{(C)} < 0.05$$

[figure not shown]
[figure not shown]
where $\mu_{(T)}$ and $\mu_{(C)}$ denote the mean distance VA for PRECISION1 and Biotrue, respectively, on the logMAR scale.

4.3 Statistical Methods for Effectiveness Analyses

4.3.1 Primary Effectiveness Analysis

A mixed effects repeated measures model will be utilized to test these hypotheses. The model will include terms for lens, period, and sequence. Within-subject correlation due to eye and the crossover design will also be accounted for in the model. Lens difference (PRECISION1 minus Biotrue) and the corresponding one-sided 95% upper confidence limit will be computed. Noninferiority in distance VA will be declared if upper confidence limit is less than 0.05.

5 SAFETY ANALYSIS STRATEGY

The focus of the safety analysis will be a comprehensive descriptive assessment of occurrence of adverse events as well as the other listed parameters. Therefore, no inferential testing will be done for the safety analysis.

5.1 Safety Endpoints

The safety endpoints are

- Adverse events (AE)
- Biomicroscopy Findings/Slit Lamp Examinations
 - Limbal hyperemia
 - Bulbar hyperemia
 - Corneal staining
 - Conjunctival staining
 - Palpebral conjunctival observations
 - Corneal epithelial edema
 - Corneal stromal edema
 - Corneal vascularization
 - Conjunctival compression/indention
 - Chemosis
 - Corneal infiltrates

- Other findings
- Device deficiencies

5.2 Safety Hypotheses

There are no formal safety hypotheses in this study. The focus of the safety analysis will be a comprehensive descriptive assessment of safety endpoints listed in Section 5.1.

5.3 Statistical Methods for Safety Analyses

The analysis set for all safety analyses is defined in Section 2.1. Baseline will be defined as the last measurement prior to exposure to study lenses. For biomicroscopy data, baseline will be defined as Visit 1 for Period 1 and Visit 2 for Period 2. Safety variables will be summarized descriptively.

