## **10 STUDY PROCEDURES AND ASSESSMENTS**

Subjects will be expected to attend 3 office visits, as shown below.

Visit #	Visit Type	Visit Window
Visit 1	Screening/Baseline/Dispense Lens 1	N/A
Visit 2	Week 1 Follow-up Lens 1/Dispense Lens 2	8 (-0/+3) days after Visit 1
Visit 3	Week 1 Follow-up Lens 2/Exit	8 (-0/+3) days after Visit 2

Unscheduled Visits and Early Exit Visits are allowed, if necessary.

Study lenses will be provided to the subjects to take home for daily wear during the course of the trial.

Study randomization will occur at Visit 1 with assigned lenses provided to take home at Visit 1 and Visit 2. Study contact lens fitting will occur at Visit 1 for both study lenses. If a subject cannot be successfully fit (either study lens) according to the study lens fitting guides as determined by the investigator, they will be required to exit from the study.

Lubrication/rewetting drops will not be permitted during this study.

Study tests, procedures, and questionnaires will be conducted as outlined in the MOP.

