## **12.6 Safety Analyses**

The safety endpoints are:

- AEs
- Biomicroscopy findings
- Device Deficiencies

There are no safety hypotheses planned in this study. The focus of the safety analysis will be a comprehensive descriptive assessment of occurrence of adverse events as well as the other listed parameters.

All AEs occurring from the time a subject signs informed consent to study exit will be accounted for in the reporting. Safety analyses will be conducted using the safety analysis set on a treatment-emergent basis. Descriptive summaries (frequencies and percentages) for ocular and nonocular AEs will be presented by Medical Dictionary for Regulatory Activities Preferred Terms. AEs leading to study discontinuation and SAEs will be identified. Individual subject listings will be provided, as necessary.

Individual subject listings will be provided for AEs that occur after signing informed consent but prior to exposure to IP, as well as for AEs that occur between treatment periods.

Each biomicroscopy parameter will be tabulated by its grade. For each biomicroscopy parameter, counts and percentages of eyes that experience an increase of  $\geq 2$  grades from baseline (last assessment prior to study lens exposure) to any subsequent visit within the same period will be presented. A supportive listing will be generated which will include all biomicroscopy data from all visits within the same period for those eyes experiencing the increase.

[figure not shown]
Two listings for device deficiencies, prior to exposure to study contact lenses and treatment-emergent, will be provided. Additionally, each device deficiency category will be tabulated.

No inferential testing will be conducted for the safety analyses.

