5.3.2 Biomicroscopy Findings/Slit Lamp Examination

The following tables and supportive listings will be provided:

- Frequency and Percentage for Biomicroscopy Findings by Visit
- Incidence of Increased Severity by 2 or More Grades in Biomicroscopy Findings
- Listing of Subjects With Other Biomicroscopy Findings
- Listing of Subjects With Conjunctival Compression/Indentation or Chemosis
- Listing of Subjects With Increased Severity by 2 or More Grades in Biomicroscopy Findings [This listing will include all relevant visits within the crossover period]
- Listing of Subjects with Infiltrates

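### Does taking Visit 2 as the Period 2 biomicroscopy baseline make the two-grade count unsound for the lens worn second?

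*SAP*

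**What the plan says.** SAP 5.3 fixes the reference examination by period: "For biomicroscopy data, baseline will be defined as Visit 1 for Period 1 and Visit 2 for Period 2". Protocol 12.6 defines the count in the same way. A rise of two or more grades is measured "from baseline (last assessment prior to study lens exposure) to any subsequent visit within the same period will be presented", and the supportive listing is to show "all biomicroscopy data from all visits within the same period for those eyes experiencing the increase". SAP 5.3.2 repeats that restriction ("This listing will include all relevant visits within the crossover period") and also plans a table titled "Frequency and Percentage for Biomicroscopy Findings by Visit".

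The visit table in Protocol 10 labels Visit 2 "Week 1 Follow-up Lens 1/Dispense Lens 2" and places it 8 to 11 days after Visit 1. Protocol 7.1 adds that on the day before Visits 2 and 3 "subjects will be instructed to wear the study lenses at least 16 hours". The lens-free interval in the same section is "of at least 12 hours will be required after Visit 1 and after Visit 2"; the start of that sentence is redacted. The schedule in Protocol Table 3-1 shows biomicroscopy at Visits 1, 2 and 3, with no further scheduled examination between Visit 2 and wear of the second lens.

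**The concern.** One examination does two jobs. At Visit 2 the eye has just had at least 8 days of the first lens, ending with a long day of wear, and in the visible text the lens-free interval comes after that examination. The Period 2 count therefore measures the second lens against the state that the first lens left behind.

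Two grade patterns show the effect. An eye graded 0-2-2 at Visits 1, 2 and 3 is counted for the first lens and not for the second, even if the second lens would have caused the same rise alone. An eye graded 0-1-2 has risen by two grades over the study but is counted and listed for neither lens. If such eyes were common, the safety summary would make the lens worn second look milder than it is. A supportive count from Visit 1 seems a cheap way to reveal this, since the grades are already collected.

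**Working it through.** The plan gives no figure for biomicroscopy grades, so there is none to reproduce. The inputs from the documents are the completion target of 116 subjects (SAP Table 1-1), which gives 116 x 2 = 232 eyes per lens, and 1:1 allocation to two sequences (Protocol 9.3), so each lens is worn second by half the subjects. The grading scale, reaction rates, overlap and persistence below are assumptions.

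**Step 1: which patterns are missed.** Assume a 0-4 scale and grade 0 at Visit 1. There are 5 x 3 = 15 paths with Visit 3 at grade 2 or more. The Period 2 count flags 6 (0-0-2, 0-0-3, 0-0-4, 0-1-3, 0-1-4, 0-2-4) and misses 9. Of those 9, 8 have grade 2 or more at Visit 2 and so are already counted for the first lens. One, 0-1-2, is counted for neither. These are numbers of patterns, not probabilities.

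**Step 2: the planned count.** Let p be a lens's true rate of two-grade rises and o the share of eyes that rise with both lenses. When worn first, a lens is counted at p. When worn second, it is counted at p - o, treating every overlapping eye as lost. Averaged over the sequences, the reported rate is p - o/2.

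- At 5% for both lenses (11.6 eyes each): o = 0.25% (independent), 2.5% and 5% give 4.875%, 3.75% and 2.5%, or 11.3, 8.7 and 5.8 eyes of 232. The share lost runs from near zero to one half.
- The loss o/2 is the same for both lenses, so the difference pA - pB is unchanged.

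**Step 3: a count from Visit 1.** Let u be the share of eyes that reacted only to the first lens and are still raised at Visit 3. The reported rate for a lens becomes p + u(q - o)/2, where q is the other lens's rate. The difference between lenses becomes (pA - pB)(1 - u/2). It is right if u = 0 and halved if u = 1.

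| True rates 10% and 4% | Lens A | Lens B | Difference | Ratio |
|---|---|---|---|---|
| Truth | 10% | 4% | 6 points | 2.5 |
| Planned, independent (o = 0.4%) | 9.8% | 3.8% | 6 points | 2.6 |
| Planned, half overlap (o = 2%) | 9% | 3% | 6 points | 3.0 |
| Planned, full overlap (o = 4%) | 8% | 2% | 6 points | 4.0 |
| From Visit 1, independent, u = 1 | 10 + 3.6/2 = 11.8% | 4 + 9.6/2 = 8.8% | 3 points | 1.3 |
| From Visit 1, full overlap, u = 1 | 10 + 0 = 10% | 4 + 6/2 = 7% | 3 points | 1.4 |

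At 5% for both lenses with independent reactions, the planned count is low by 0.125 points. The Visit 1 count is high by up to (5 - 0.25)/2 = 2.375 points (17.1 eyes instead of 11.6), which is 19 times as much.

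**Step 4: allow one-grade rises.** Step 2 ignores eyes that the first lens raises by one grade only. Suppose each lens independently raises 20% of eyes by one grade and 5% by two. The second lens is then counted only where the first caused no rise: 232 x 0.05 x 0.75 = 8.7 eyes in Period 2, against a true 11.6. The Visit 1 count gives 11.6 if nothing persists and 232 x (1 - 0.95 x 0.95) = 22.6 if everything does. It would still assign up to 11.6 eyes to a second lens that caused nothing.

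With unequal lenses (A: 30% by one grade, 10% by two; B: 10% and 2%), the planned count loses 10% x 0.12/2 = 0.6 points for A and 2% x 0.40/2 = 0.4 points for B. It reports 9.4% and 1.6%, a difference of 7.8 points against a true 8. So the difference is no longer kept exactly, but it moves by only 0.2 points. The Visit 1 count with full persistence gives 10.9% and 6.9%, a difference of 4 points.

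**The case for a change.** The best case for a change is that it costs little and fills a real gap. The by-visit table shows grade frequencies, not change within an eye. The two-grade listing covers only eyes flagged in that period. The adverse event route (Protocol 11.1) depends on the investigator judging the change clinically relevant. Infiltrates, chemosis, compression and other findings have their own listings, but hyperemia, staining, edema and vascularization do not. SAP 4 plans a look by period if carryover appears in the effectiveness data, and the visible biomicroscopy text has no counterpart. A Visit 1 count beside the planned one, with all three visits listed for every flagged eye, would use data already in hand.

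Part of this stands. The absolute rate for the lens worn second can be understated, and no eye-level biomicroscopy output picks out a 0-1-2 eye for those four kinds of sign.

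The rest does not. A Visit 1 count would not reveal the undercount, because an eye graded 0-2-2 looks the same whether the second lens caused a reaction or a finding from the first lens persisted. A three-visit listing prints the same three grades in both cases. The ratio, which the planned count does distort, is not a planned output; Protocol 12.6 asks for counts and percentages. Visit 1 is not a clean reference either, since subjects arrive as habitual lens wearers (Protocol 8.1). Because the sentence on the lens-free interval is partly redacted, an interval before the Visit 2 examination cannot be ruled out.

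**Conclusion.** The plan stands as written. A baseline for each period is an accepted crossover choice, and Protocol 12.6 and SAP 5.3 agree on it. The count is descriptive, and study success rests on distance visual acuity alone.

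The understatement is possible, but its size cannot be taken from the documents: under the two-state model of Step 2 it runs from nearly none to half of a lens's events, depending on an overlap that has to be assumed. In that model the planned count keeps the difference between lenses; with one-grade rises allowed, the difference moved by 0.2 points in the case worked. The Visit 1 count is better only if findings from the first lens clear by Visit 3. If they persist, it can halve the difference and so hide the worse lens. That is a trade-off, and nothing in the documents favours the alternative. Most eyes at issue are visible already: a 0-2-2 eye is counted and listed in Period 1, and Visit 3 grades are tabulated. If a reader of the report wants the eye-level picture, the collected grades allow a cross-tabulation of the three visits by sequence without any change to the plan.
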